11.2.2. Dose number

- The study dose number is defined in reference to the number of study visits at which vaccination occurred. More specifically dose 1 refers to all vaccines administered at the first vaccination visit while dose 2 corresponds to all vaccinations administered at the second vaccination visit even if this is the first time a product is administered to the subject.
- Relative dose: the relative dose for an event (AE, medication, vaccination) is the most recent study dose given before an event. In case the event takes place on the day a study dose is given, the related dose will be that of the study dose, even if the event actually took place before vaccination. For instance, if an adverse event begins on the day of the study vaccination but prior to administration of the vaccine, it will be assigned to this dose. In case a study dose is not administered and an event occurs after the subsequent study dose (eg 3rd study dose), the relative dose of the event will be study dose associated to the subsequent study dose (eg dose 3).
 - The number of doses for a product is the number of time the product was administered to a subject.
 - The incidence per dose is the number of vaccination visits at which an event was reported among all vaccination visits.

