 - For the Control group, the occurrence of solicited general AEs over a 7-day follow-up period (day of administration and 6 subsequent days) after administration of Vitamin A at 6 months of age (Visit 2).
 - For the Coad and the RTS,S groups, the occurrence of solicited local and general AEs over a 7-day follow-up period (day of vaccination and 6 subsequent days) after dose of study vaccines administered at 7.5 months of age (Visit 3).
 - For the Control group, the occurrence of solicited general AEs over a 7-day follow-up period (day of visit and 6 subsequent days) after Visit 3 (7.5 months of age).
 - For all groups, the occurrence of solicited general and local AEs over a 14-day follow-up period (day of vaccination and 13 subsequent days) after dose of study vaccines administered at 9 months of age (Visit 4).
- Unsolicited AEs.
 - For all groups, the occurrence of unsolicited AEs over a 30-day follow-up period (day of administration and 29 subsequent days) after administration of Vitamin A and study vaccines at 6 months of age (Visit 2).
 - For the Coad and the RTS,S groups, the occurrence of unsolicited AEs over a 30-day follow-up period (day of vaccination and 29 subsequent days) after dose of study vaccines administered at 7.5 months of age (Visit 3).
 - For the Control group, the occurrence of unsolicited AEs over a 30-day follow-up period (day of visit and 29 subsequent days) after Visit 3 (7.5 months of age).
 - For all groups, the occurrence of unsolicited AEs over a 42-day follow-up period (day of vaccination and 41 subsequent days) after dose of study vaccines administered at 9 months of age (Visit 4).
 - For the Coad and the RTS,S groups, the occurrence of unsolicited AEs over a 30-day follow-up period (day of vaccination and 29 subsequent days) after the booster dose of study vaccine administered at 27 months of age (Visit 10).
 - For the Control group, the occurrence of unsolicited AEs over a 30-day follow-up period (day of vaccination and 29 subsequent days) after dose of study vaccines administered at 10.5, 11.5, 12.5 and 30 months of age (Visit 6, 7, 8 and 12).

- SAEs: all, fatal and related SAEs.
 - The occurrence of SAEs occurring within 30 days (day of vaccination and 29 subsequent days) after each administration.
 - The occurrence of SAEs from Screening visit (Visit 1) until Month 4.5.
 - The occurrence of SAEs from Screening visit (Visit 1) until study end (Month 33 for Coad and RTS,S groups and Month 36 for the Control group).

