6.5. Analysis of safety

6.5.1. Analysis of safety planned in the protocol

The primary analysis will be based on the ES.

The percentage of subjects with at least one local AE (solicited and unsolicited), with at least one general AE (solicited and unsolicited) and with any AE during the solicited follow-up period [7 days post Dose 1, post Dose 2 and 14 days post Dose 3] will be tabulated with exact 95% CI after each vaccine dose and overall. The percentage of doses followed by at least one local AE (solicited and unsolicited), by at least one general AE (solicited and unsolicited) and by any AE will be tabulated for the overall vaccination course, with exact 95% CI. Similar tables will be generated for Grade 3 AEs and AEs considered as causally related to vaccination.

The percentage of subjects reporting each individual solicited local and general AE during the solicited follow-up period will be tabulated with exact 95% CI. The percentage of doses followed by each individual solicited local and general AE will be tabulated for each dose and for the overall vaccination course, with exact 95% CI. Similar tables will be generated for Grade 3 AEs, causal events and for fever, temperature in 0.5°C increments.

The proportion of subjects reporting an AE (unsolicited) until 30 days (Days 0-29) post each dose of RTS,S/AS01_E, classified by the Medical Dictionary for Regulatory Activities (MedDRA) preferred term level will be tabulated with exact 95% CI. The proportion of subjects reporting an AE (unsolicited) until 42 days (Days 0-41) after the administration of the YF vaccine and the combined measles and rubella vaccine (restricted to the Coad group and Control group), classified by the MedDRA preferred term level will be tabulated with exact 95% CI. Similar tables will be generated for Grade 3 AEs and AEs considered as causally related to vaccination.

The proportion of subjects reporting an SAE (all, fatal, related) occurring within 30 days (day of vaccination and 29 subsequent days) after each visit where a study product is potentially administered, classified by the MedDRA preferred term level will be tabulated with exact 95% CI.

The proportion of subjects reporting an SAE (all, fatal, related) from Day 0 to Month 4.5 and over the whole study duration (Day 0 to Month 33 for Coad and RTS,S groups and Month 36 for the Control group), classified by the MedDRA preferred term level will be tabulated with exact 95% CI.

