The proportion of subjects reporting an AEs of specific interest (pIMDs, meningitis and seizures) from Day 0 to Month 4.5 and over the whole study duration (Day 0 to Month 33 for Coad and RTS,S groups and Month 36 for the Control group), classified by the MedDRA preferred term level will be tabulated with exact 95% CI.

For generalized convulsive seizures occurring within 7 days after vaccines administered at Visit 2 and 3 (Coad and RTS,S groups) and 14 days after vaccines administered at Visit 4 (all groups) an analysis will be performed based on the Brighton Collaborations guidelines [**Bonhoeffer**, 2004]. This includes descriptive tables of the time relationship of seizures to vaccination, the duration of seizures and the level of diagnostic certainty.

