11.2. Standard data derivation

11.2.1. Date derivation

- SAS date derived from a character date: In case day is missing, 15 is used. In case day & month are missing, 30June is used.
- The onset day for a safety event is the number of days between the last study vaccination and the onset/start date of the event (onset date – last study vaccination+1). This is 1 for an event starting on the same day as a vaccination.
- Duration: Duration of an event is expressed in days. It is the number of days between the start & the stop dates + 1. Therefore duration is 1 day for an event starting & ending on the same day.

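### SAP Section 11 numbers doses and onset days by vaccination, which does not fit Control Visits 2, 3 and 4, and elimination code 1030 conflicts with the Exposed Set definition

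*SAP*

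**What the plan says.** The SAP's Section 6 refers the reader to Section 11 for derivation rules and does not repeat them, so Section 11 is the operative text.

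- **Dose number (11.2.2).** Doses are counted by vaccination visits: "dose 1 refers to all vaccines administered at the first vaccination visit". Per-dose incidence follows suit: "The incidence per dose is the number of vaccination visits at which an event was reported among all vaccination visits".
- **Onset day (11.2.1).** "The onset day for a safety event is the number of days between the last study vaccination and the onset/start date of the event", plus one.
- **Control schedule (Protocol Section 3 and Table 12).** Vitamin A at Visit 2, no product at Visit 3, yellow fever and measles-rubella vaccines at Visit 4, then RTS,S/AS01E at Visits 6, 7, 8 and 12.
- **Endpoints (SAP 4.2).** For Control these are defined by visit, for example "solicited general AEs over a 7-day follow-up period (day of visit and 6 subsequent days) after Visit 3" and "unsolicited AEs over a 30-day follow-up period (day of visit and 29 subsequent days) after Visit 3". At Visit 4 the solicited period is 14 days in all groups.
- **Analysis windows (SAP 6.5.1).** The by-dose periods are "7 days post Dose 1, post Dose 2 and 14 days post Dose 3".
- **Mock tables (SAP Annex 3).** Templates 26, 28 and 34 leave Control cells open for general symptoms at Doses 1 and 2, with a 14-day period at Dose 3.
- **Denominators (SAP 11.2.5).** The per-dose N requires that study vaccine was given at the visit. For unsolicited events, the text counts children who received Vitamin A, but the N table names study vaccine recipients only.
- **Exposed Set (SAP 5.1.2, 5.2.1, 5.2.2.1 and Annex 2).** The definition admits a child who received Vitamin A alone. Code 1030, which removes children from the set, is worded as study vaccine never given.

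**The concern.** Coad and RTS,S children are vaccinated at Visits 2, 3 and 4, so for them dose number and visit coincide. Control children are not vaccinated until Visit 4. A programmer who follows Section 11 cannot fill the Control Dose 1, 2 and 3 rows as the tables intend, and must improvise the mapping and the overall/dose denominator.

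Two labels add to this. The code 1030 wording would drop Control children who took Vitamin A and left before Visit 4. The unsolicited N label would drop the same children from the denominator. Control is a comparator column in these safety tables, so its percentages should not depend on an unstated programming choice.

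**Working it through.** **Inputs.** 233 children per group (Protocol 10.4, SAP Table 1). As a check, 205 / (1 - 0.12) = 232.95, which rounds to the plan's 233. Product schedule from Protocol Section 3. The minimum interval from Visit 2 to Visit 3 is 28 days (Protocol Table 7), and the nominal 1.5 months is about 46 days.

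**Step 1: apply the dose-number rule to Control.**

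| Reading | Dose 1 | Dose 2 | Dose 3 | Visit 3 |
|---|---|---|---|---|
| Vaccines only (as worded) | Visit 4 | Visit 6 | Visit 7 | no number |
| Vitamin A counted | Visit 2 | Visit 4 | Visit 6 | no number |
| Needed by 6.5.1 and Templates 26, 28, 34 | Visit 2 | Visit 3 | Visit 4 | Dose 2 |

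Neither reading of the rule gives the third line.

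**Step 2: window at Visit 4.** Section 6.5.1 gives 7, 7 and 14 days for Doses 1, 2 and 3. Control Visit 4 is Dose 1 or Dose 2 under the rule, so its window is 7 days. SAP 4.2 asks for 14. The 14-day window would attach to Visit 7 or Visit 6, where no solicited events are collected in Control.

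**Step 3: onset day after Visit 3.** If only vaccines count, there is no prior vaccination and the onset day is undefined. If Vitamin A counts, it runs from Visit 2. For the seven days starting at Visit 3:

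- minimum gap: 28 + 1 = 29 to 28 + 7 = 35;
- nominal gap: 46 + 1 = 47 to 46 + 7 = 53.

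All lie outside Days 1-7. With a visit-based index they are Days 1 to 7 of Visit 3.

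**Step 4: overall/dose denominator through Visit 4.** The template footnotes define this N as administered doses.

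- Coad and RTS,S: 233 x 3 = 699 in each group (the same figure as total enrolment, by coincidence).
- Control, vaccines only: 233 x 1 = 233.
- Control, Vitamin A counted: 233 x 2 = 466.

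For illustration, let p2 and p4 be the proportions with a general symptom after Visits 2 and 4. The figure is p4 on N = 233 and (p2 + p4)/2 on N = 466, so the ratio is 2 x p4 / (p2 + p4). The documents give no incidences. Assuming p2 of 5-20% and p4 of 20-40%, the ratio runs from 1.0 (20% and 20%) to 1.78 (5% and 40%: 40.0% against 22.5%).

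**Step 5: labels.** The Exposed Set definition admits Vitamin A or study vaccine, while code 1030 tests study vaccine alone. A Control child who leaves between Visits 2 and 4 is in by the first and out by the second. The number of such children is not given. The Per-Protocol Set is unaffected, because an incomplete vaccination course already excludes them.

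**The case against.** The case for leaving the text alone is substantial.

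- The endpoints in SAP 4.2 are already visit-based, and so is the 30-day SAE analysis in 6.5.1, which runs from each visit where a product may be given.
- The templates are declared illustrative, were copied from another study and are to be adapted through a table of contents that is not part of these documents. Template 30 already sets Control Doses 1 and 2 to not applicable.
- The intent can be inferred. SAP 6.1.1 lets Vitamin A stand for first vaccination in Control, and Template 25 has a Vitamin A row.
- A sentence in 11.2.2 treats dose number as a scheduled position: "In case a study dose is not administered and an event occurs after the subsequent study dose (eg 3rd study dose".
- By-dose rows count subjects, and the per-subject N for solicited general symptoms carries no vaccine condition.
- Diary cards are tied to Visits 2 and 3 (Protocol Table 6), so solicited events keep their visit link.
- Code 1030 is a short label, and detailed elimination criteria sit in a separate document (SAP 5.2).

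Most of this stands and limits the effect, but it does not remove the gap. The missed-dose sentence concerns a dose that was not administered, whereas Control has none scheduled at Visit 3. At best it preserves the Dose 3 label at Visit 4. Counting Vitamin A repairs Visit 2 but leaves Visit 3 unnumbered and makes Visit 4 Dose 2. The SAP adapted its wording for Control in 6.1.1, in the SAE window and in the unsolicited text, but not in 11.2.1, 11.2.2, the N table or code 1030.

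**Conclusion.** Wrong as written, and minor. The dose-number and onset-day rules do not produce the Control by-dose rows. Visit 3 fails on either reading, and Visit 4 would take a 7-day window where 14 days are intended. The per-dose N affects only Control's overall/dose figure: nominally 233 or 466, assuming full attendance. Any resulting percentage difference depends on incidences that the documents do not give. Code 1030 contradicts the Exposed Set definition, with an unknown number of children affected.

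A reader might infer more, but the documents do not support it:

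- *Control safety data after Visits 2 and 3 would be lost.* They are collected, and their endpoints are defined by visit. Only the derivation text fails to place them.
- *Denominators in the by-dose rows are wrong.* Those rows count subjects, so the per-dose N does not govern them.
- *Vitamin A recipients are left out of the unsolicited analysis.* The 11.2.5 text includes them. This is a contradiction between that text and its N table.
- *Control's overall/dose N should be 699.* That would count Visit 3 as an administered dose, against the template footnotes.
- *The safety objective or the non-inferiority tests are compromised.* Coad and RTS,S are mapped correctly through Visit 4, and these rules enter no non-inferiority test or power figure.

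**What to change.** Amend the SAP as follows.

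(a) In 11.2.1 and 11.2.2, index Dose 1, 2 and 3 and onset day to scheduled Visits 2, 3 and 4 in all groups for the by-dose tables. Number Control's later RTS,S/AS01E course (Visits 6, 7, 8 and 12) separately.

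(b) For Control overall/dose, use the visits at which a study vaccine or Vitamin A was given (Visits 2 and 4) in both numerator and denominator, a nominal N of 466. Report Visit 3 only in its by-visit row.

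(c) In the 11.2.5 N table, set the unsolicited N to all Exposed Set subjects, to match the text of that section.

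(d) Reword code 1030, wherever it appears, to mean that neither study vaccine nor Vitamin A was administered.

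The cost is a few sentences of SAP wording and the matching derivation programs. No new data are needed.

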11.2.3. Demography

- Age: Age at the reference activity, computed as the number of days between the date of birth and the reference activity and converted in months (= days *12 /365.25) (keeping 1 decimal digit).

11.2.4. Immunogenicity

- For a given subject and given immunogenicity measurement, missing or non-evaluable measurements will not be replaced. Therefore, an analysis will exclude subjects with missing or non-evaluable measurements.
- The Geometric Mean Concentrations/Titres (GMC/Ts) calculations are performed by taking the anti-log of the mean of the log titre transformations (base 10). Antibody titres below the cut-off of the assay will be given an arbitrary value of half the cut-off of the assay for the purpose of GMT calculation. The cut-off value is defined by the laboratory before the analysis.
- A subject seropositive for anti-CS antibody will be a subject whose antibody titre will be greater than or equal to the cut-off value (anti-CS \geq 1.9 EU/ml).
- A subject seropositive for anti-HBs antibody will be a subject whose antibody titre will be greater than or equal to the cut-off value (anti-HBs \geq 6.2 mIU/ml).
- Seroprotection rate for anti-HBs antibody is defined as the percentage of subjects with antibody titres greater than or equal to 10 mIU/ml (anti-HBs \geq 10 mIU/ml).

- Seroconversion rate for anti-Me is defined as the percentage of children with an anti-Me pre-vaccination titre below 150 mIU/ml and a post-vaccination titre \geq 150 mIU/ml (i.e. the subject is seropositive post-vaccination and seronegative pre-vaccination for anti-Me).
- Seroconversion rate for anti-Ru is defined as the percentage of children with an anti-Ru pre-vaccination titre below 4 IU/ml and a post-vaccination titre \geq 4 IU/ml (i.e. the subject is seropositive post-vaccination and seronegative pre-vaccination for anti-Ru).
- Seroprotection rate for anti-Ru antibody is defined as the percentage of subjects with antibody titres greater than or equal to 10 IU/ml (anti-Ru \geq 10 IU/ml).
- A subject seropositive for anti-YF antibody will be a subject whose antibody titre will be greater than or equal to the cut-off value (anti-YF \geq 10 ED50).
- A subject seropositive for anti-catalase antibody will be a subject whose antibody concentration is greater than or equal to 65 ng/ml.
- The assay cut-off is the value under which there is no quantifiable result available. For an assay with a specific 'cut_off' , numerical immuno result is derived from a character field (rawres):
 - If rawres is 'NEG' or '-' or '(-)', numeric result= cutt_off/2,
 - if rawres is 'POS' or '+' or '(+)', numeric result = cut_off,
 - if rawres is '< value' and value \leq cut_off, numeric result =cut_off/2,
 - if rawres is '< value' and value $>$ cut_off, numeric result =value,
 - if rawres is '> value' and value $<$ cut_off, numeric result =cut_off/2,
 - if rawres is '> value' and value \geq cut_off, numeric result =value,
 - if rawres is '<= value' or '>= value' and value $<$ cut_off, numeric result =cut_off/2,
 - if rawres is '<= value' or '>= value' and value \geq cut_off, numeric result =value,
 - if rawres is a value $<$ cut_off, numeric result = cut_off/2,
 - if rawres is a value \geq cut_off, numeric result = rawres,
 - if rawres is a value \geq cut_off, numeric result = rawres,
 - else numeric result is left blank.
 - All CI computed will be two-sided 95% CI.

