10.4. Determination of sample size

For the primary endpoint, with 205 evaluable subjects per group the study has at least 90% power to rule out a minimum 2-fold decrease in anti-CS GMTs in the Coad group versus the RTS,S group with a 2-sided 5% alpha level and an assumed anti-CS log standard deviation of ≤ 0.9 (see [Table 19](#)).

For the secondary endpoints, the power to demonstrate non-inferiority in terms of anti-YF, anti-Ru and anti-Me with 205 evaluable subjects per group is presented in [Table 19](#). Non-inferiority is defined as the UL of the 95% CI on the difference (Control group minus Coad group) in response $<10\%$.

In order to account for drop-outs and subjects non-evaluable for immunogenicity endpoints (approximately 12%), 233 subjects per group will be enrolled for a total of 699 subjects.

Table 19 Sample size and power

Antibody	Endpoint	Non-inferiority limit	Reference in control	Power
Anti-CS	GMT ratio (RTS,S group / Coad group)	2-fold decrease	log SD ≤ 0.9	90%
Anti-Ru	Seroconversion	10%	90%*	90%
Anti-YF	Seropositivity	10%	95%**	99%
Anti-Me	Seroconversion	10%	90%**	90%

Power of a non-inferiority test on seroconversion/positivity or means, 2-sided alpha 0.05, N=205 (Pass 2005).

* Adapted from Rubella vaccines: WHO position paper [[WHO](#), 2011].

** [[GlaxoSmithKline Biologicals Clinical Study Report Amendment 1 - 106369](#) (MALARIA-050)].

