10.6. Derived and transformed data

- A subject seropositive for anti-CS antibody will be a subject whose antibody titer will be greater than or equal to the cut-off value (anti-CS ≥ 0.5 EU/ml).

- Seroprotection rate for anti-HBs antibody is defined as the percentage of subjects with antibody titers greater than or equal to an established cut-off (anti-HBs ≥ 10 mIU/ml).
- Seroconversion rates for anti-Me is defined as children with an anti-Me pre-vaccination titer below 150 mIU/ml and a post-vaccination titer ≥ 150 mIU/ml.
- Seroconversion rates for anti-Ru is defined as children with an anti-Ru pre-vaccination titer below 4 IU/ml and a post-vaccination titer ≥ 4 IU/ml.
- A subject seropositive for anti-YF antibody will be a subject whose antibody titer will be greater than or equal to the cut-off value (anti-YF ≥ 10 ED50).
- A subject seropositive for anti-catalase antibody will be a subject whose antibody concentration is greater than or equal to 65 ng/ml.
- The GMT calculations will be performed by taking the anti-log of the mean of the log transformations (base 10). Antibody titers below the cut-off of the assay will be given an arbitrary value of half the cut-off for the purpose of GMT calculation. All available immunogenicity data will be analyzed. Missing data will not be imputed.

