6. STATISTICAL ANALYSES

Note that standard data derivation rule and stat methods are described in Section 11 and will not be repeated below.

All statistical analyses will be performed using SAS 9.2 or later versions.

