6.4. Immunogenicity

6.4.1. Analysis of immunogenicity planned in the protocol

The primary analysis will be based on the PPS for immunogenicity.

For the primary endpoint, the 95% CIs of the anti-CS GMT ratio between the groups (RTS,S group over Coad group) at one month post Dose 3 of RTS,S/AS01_E will be calculated. Non-inferiority of anti-CS immune response will be concluded if the UL of this CI is below 2.

For the secondary endpoints, the 95% CIs of the difference in anti-Me, anti-Ru and anti-YF seroconversion/seropositivity rates between the groups (Control group minus Coad group) at one month post-vaccination will be calculated (standardized asymptotic). The seroconversion rate is defined as the percentage of initially seronegative that are seropositive post-vaccination. Non-inferiority will be concluded if the UL of this CI is below 10%.

The percentage of subjects with seropositive levels of anti-CS (proportion of subjects with anti-CS antibody titres ≥ 1.9 EU/ml) with 95% CI will be determined at Day 0 and one month post Dose 3 of RTS,S/AS01_E in the RTS,S group and Coad group. Antibody titres will be summarized by GMT with 95% CI. Antibody titres at one month post Dose 3 of RTS,S/AS01_E will also be investigated using reverse cumulative curves.

Seroprotection level for anti-HBs with 95% CI will be determined at Day 0 and one month post Dose 3 of RTS,S/AS01_E in the RTS,S group and Coad group. Anti-HBs titres will be summarized by GMT with 95% CI. Anti-HBs titres one month post Dose 3 of RTS,S/AS01_E will also be investigated using reverse cumulative curves.

Seropositivity levels of anti-Ru (≥ 4 IU/ml) and seropositivity levels of anti-Me (≥ 150 mIU/ml) with 95% CI will be determined pre-vaccination and one month post-vaccination with the YF vaccine and the combined measles and rubella vaccine in the Control group and Coad group. Antibody titres will be summarized by GMT with 95% CI. Anti-Ru and anti-Me titres at one month post-vaccination with the YF vaccine and the combined measles and rubella vaccine will also be investigated using reverse cumulative curves.

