13. ANNEX 3: STUDY SPECIFIC MOCK TFL

The following drafted study specific mocks will be used.

The data display, title and footnote is for illustration purpose and will be adapted to the study specificity as indicated in the TFL TOC. These templates were copied from MALARIA-063 and additional tables required for public disclosure were added.

Note that there may be few changes between the study specific SAP mock TFL and the final TFLs as editorial/minor changes do not require a SAP amendment.

Template 1 Number of subjects enrolled by center, per study group (Exposed Set)

Center	Coad N =		RTS,S N =		Control N =		Total N =	
	n	%	n	%	n	%	n	%
PPD (Ghana)								
PPD (Ghana)								

Coad =

RTS,S =

Control =

N = Number of subjects

n = Number of subjects enrolled by center

Center = GSK Biologicals assigned center number

% = n / Number of subjects with available results x 100

Template 2 Number of enrolled subjects by country (All Enrolled Set)

Country	Coad N =	RTS,S N =	Control N =	Total N =
	N	n	n	n
Ghana				

Coad =

RTS,S =

Control =

N = number of subjects

n= number of enrolled subjects included in each group or in total

Template 3 Number of enrolled subjects by age category (All Enrolled Set)

Characteristics	Categories	Coad N =	RTS,S N =	Control N =	Total N =
		n	n	n	n
Age category	Infants and toddlers (28 days-23 months)				

Coad =

RTS,S =

Control =

N = Number of enrolled subjects

n= number of enrolled subjects included in each group or in total for a given age category or for all age categories

Missing = <describe missing>

Template 4 Consort, per study group (Month 4.5)(all screened set)

	Total	Coad	RTS,S	Control
Screened				
Reasons for not being vaccinated				
Did not meet eligibility criteria				
Migrated/Lost to FU before first vaccination				
Other				
Protocol violation				
Vaccinated (at least one vaccination)				
Reasons for incomplete vaccination course				
Other				
Protocol violation				
Serious adverse event				
Subjects with full vaccination course				
Reasons for elimination from PPS for immunogenicity				
Serological results not available				
Administration of concomitant vaccination				
Wrong replacement				
Inclusion criteria not met				
Out of interval				
PPS for immunogenicity				

Coad =

RTS,S =

Control =

Template 5 Number of subjects vaccinated, completed and withdrawn with reason for withdrawal until Month 4.5, per study group (Exposed Set)

	Coad	RTS,S	Control	Total
Number of subjects vaccinated				

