N = Number of times each eligibility criterion was reported as a reason for a subject failing screening

Note: Subjects could fail multiple eligibility criteria. Therefore, the sum of N in this table is greater than the number of subjects that were screening failures due to not meeting the eligibility criteria

LAR : Legally Acceptable Representative

ICF : Informed Consent Form

Template 13 Primary objective assessment: Non-inferiority assessment of anti-CS antibody response to RTS,S/AS01E in Coad and RTS,S groups, GMT ratio, Month 4 (Per-Protocol Set)

Antibody	RTS,S		Coad		GMT ratio (RTS,S / Coad)		
	N	GMT	N	GMT	Value	LL	UL
Anti-CS							

RTS,S =

Coad =

GMT = geometric mean antibody titre

N = Number of subjects with post-vaccination results available

95% CI = 95% confidence interval for the GMT ratio (Anova model - pooled variance); LL = lower limit, UL = upper limit

PIII(M4) = Post Dose 3, Month 4

Template 14 Non-inferiority assessment of anti-Me and anti-Ru antibody seroconversion rates in Coad and Control groups, Differences, Month 4 (Per-Protocol Set)

							Difference in seroconversion rate (Group 1 minus Group 2)			
							95 % CI			
Antibody	Group 1	N	%	Group 2	N	%	Difference	%	LL	UL
Anti-Me	Control			Coad			Control - Coad			
Anti-Ru	Control			Coad			Control - Coad			

Control =

Coad =

N = number of subjects with available results

% = percentage of subjects with Anti-Me/Anti-Ru titre \geq . MIU-ML post-vaccination and $<$.MIU-ML pre-vaccination

95% CI = 95% Standardized asymptotic confidence interval; LL = lower limit, UL = upper limit

P_{III}(M4) = Post Dose 3, Month 4

Template 15 Non-inferiority assessment of anti-YF antibody seropositivity rate in Coad and Control groups, Difference, Month 4 (Per-Protocol Set)

						Difference in seropositivity rate (Group 1 minus Group 2)			
						95 % CI			
Group 1	N	%	Group 2	N	%	Difference	%	LL	UL
Control			Coad			Control - Coad			

Control =

Coad =

N = number of subjects with available results

% = percentage of subjects with Anti-YF titre \geq . MIU-ML

95% CI = 95% Standardized asymptotic confidence interval; LL = lower limit, UL = upper limit

P_{III}(M4) = Post Dose 3, Month 4

Template 16 Anti-CS seropositivity rates and GMTs in Coad and RTS,S groups, Month 4 (Per-Protocol Set)

			≥ 1.9 EU/ml				GMT					
			95% CI						95% CI			
Antibody	Group	Timing	N	n	%	LL	UL	value	LL	UL	Min	Max
Anti-CS	RTS,S	Pre										
		P _{III} (M4)										
	Coad	Pre										
		P _{III} (M4)										

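### The measles and rubella seroconversion rates have an explicit seronegative denominator in SAP 6.4.1 but none in the derivation rule of SAP 11.2.4, and the two readings can reverse the non-inferiority conclusion

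*SAP*

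**What the plan says.** The analysis text and the derivation text describe the rate differently.

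- **Analysis text.** SAP 6.4.1 states: "The seroconversion rate is defined as the percentage of initially seronegative that are seropositive post-vaccination". Protocol 10.8 has the same sentence. It comes immediately before the success rule, an upper 95% limit below 10% for Control minus Coad.
- **Derivation text.** SAP 11.2.4 says for measles "Seroconversion rate for anti-Me is defined as the percentage of children with an anti-Me pre-vaccination titre below 150 mIU/ml", together with a post-vaccination titre of at least 150 mIU/ml. For rubella it says "Seroconversion rate for anti-Ru is defined as the percentage of children with an anti-Ru pre-vaccination titre below 4 IU/ml", together with a post-vaccination titre of at least 4 IU/ml. Protocol 10.6 is similar: "Seroconversion rates for anti-Me is defined as children with an anti-Me pre-vaccination titer below 150 mIU/ml".
- **Link between them.** SAP section 6 sends the reader to the annex: "Note that standard data derivation rule and stat methods are described in Section 11 and will not be repeated below".
- **Mock table.** SAP Template 14, the table for these two tests, puts both the pre- and the post-vaccination condition into the percentage and footnotes the denominator as "N = number of subjects with available results". Annex 3 says of all templates: "The data display, title and footnote is for illustration purpose and will be adapted to the study specificity as indicated in the TFL TOC".

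**The concern.** In SAP 11.2.4 both conditions describe the children who are counted, and no restricted denominator is named. The seroprotection rates in the same list have the same form, and there the denominator is everyone with a result. A programmer following the annex could therefore divide by all children with Month 3 and Month 4 results.

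Nothing else in the plan makes the two rules agree. Protocol 4.3 excludes prior measles or rubella vaccination but asks for no serology. No elimination code in SAP 5.2.2.1 removes children seropositive at Month 3. Month 3 seropositivity is itself an endpoint in SAP 4.2, so the plan expects that it may occur.

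These rates decide two secondary objectives that have a pre-defined success criterion. Under the literal rule the difference is diluted, so the margin becomes looser among susceptible children. The variance also rises, so power falls. A chance imbalance in baseline seropositivity enters the comparison directly.

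**Working it through.** **Inputs from the documents.** Margin 10 points, Control minus Coad; two-sided alpha 0.05; 205 evaluable children per group; 90% reference rate and 90% stated power for anti-Me and anti-Ru (protocol 10.4, Table 19); Miettinen-Nurminen interval (SAP 6.4.2).

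**Assumption.** The seropositive share at Month 3, s, is not in the documents. I use 0, 5, 10 and 20%, equal in both groups unless stated.

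**1. Reproduce the stated power.** With 90% in both groups and n = 205, the simple normal formula gives SE = √(2 × 0.9 × 0.1 / 205) = 0.0296 and power Φ(0.10/0.0296 − 1.96) = 92.1%. The score approximation gives 90.1%, and exact enumeration of the Miettinen-Nurminen test gives 91.0%. The stated 90% is reproduced, with all 205 children per group in the denominator.

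**2. Write down both rules.** Let c be conversion among seronegatives.

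- 6.4.1 rule: rate = c, with n = 205(1 − s).
- Literal 11.2.4 rule: rate = (1 − s)c, with n = 205.

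Under the literal rule the difference is (1 − s) times the difference among seronegatives. The 10-point margin therefore acts as 10/(1 − s) points among seronegatives. At s = 10% and c = 90% the literal rate is 0.9 × 0.9 = 81%. Then SE = √(2 × 0.81 × 0.19 / 205) = 0.0387, and the simple formula gives 73.3%; the exact value is 73.1%.

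**3. Results** (exact Miettinen-Nurminen; error is the chance of passing at a true 90% vs 80% among seronegatives; disagreement is from 1,000,000 simulated trials with true 90% in both groups):

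| Seropositive at Month 3 | 0% | 5% | 10% | 20% |
|---|---|---|---|---|
| n seronegative per group | 205 | 195 | 184 | 164 |
| Power, 6.4.1 rule | 91.0% | 89.3% | 87.6% | 83.7% |
| Power, literal rule | 91.0% | 81.2% | 73.1% | 61.7% |
| Margin among seronegatives, literal rule | 10.0 | 10.5 | 11.1 | 12.5 |
| Error, 6.4.1 rule | 2.5% | 2.5% | 2.4% | 2.5% |
| Error, literal rule | 2.5% | 3.4% | 4.3% | 6.4% |
| Rules disagree | 0% | 12.1% | 19.7% | 29.4% |
| of which 6.4.1 passes, literal fails | 0% | 10.1% | 17.1% | 25.6% |

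**4. Same data, both rules** (205 per group; upper 95% limit for Control minus Coad):

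| Seropositive, Control / Coad | Converters among seronegatives, Control vs Coad | 6.4.1 rule | Literal rule |
|---|---|---|---|
| 20 / 20 | 166/185 vs 161/185 | 9.43, pass | 10.27, fail |
| 10 / 20 | 176/195 vs 166/185 | 6.80, pass | 12.16, fail |
| 20 / 10 | 166/185 vs 168/195 | 10.27, fail | 6.61, pass |

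In the second row conversion is almost equal (90.3% vs 89.7%). The literal difference of 4.88 points arises mostly from ten extra baseline seropositives in Coad.

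**The case against.** The best counter-argument is that the plan names only one denominator, and names it next to the decision rule, in identical words in both documents. SAP 11.2.4 never says all children. Its parenthetical gloss describes a single child, so it can be read as defining who is a converter, with 6.4.1 supplying the denominator. Template 14 is illustrative, copied from another study, and has blank cut-offs. This stands to the extent that the defect is an ambiguity and not a flat contradiction, and a careful programmer could get it right. It does not close the gap: section 6 defers to section 11 for derivations, no text gives 6.4.1 precedence, and the one mock table for these tests leans the other way.

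A second objection is that most of the harm is conservative. In the simulations with equal true conversion, roughly 85% of disagreements are trials that 6.4.1 passes and the literal rule fails (for example 25.6 of 29.4 points at 20%). That is correct for that scenario. But error at the margin also rises, and an imbalance in baseline seropositivity can produce a pass that 6.4.1 would refuse, as the third row of the last table shows.

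A third is that the size rests on an undocumented seropositive share. That is true, and at 0% there is no effect.

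Finally, protocol 10.4 refers to "the power to demonstrate non-inferiority in terms of anti-YF, anti-Ru and anti-Me with 205 evaluable subjects per group is presented in", and evaluable could be taken to mean seronegative. This is a fair reading, so a note to Table 19 is optional.

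**Conclusion.** The concern holds and should be fixed. The derivation rule leaves open the denominator of two tests that carry a success criterion, and the literal reading departs from the definition in SAP 6.4.1 and protocol 10.8.

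The size rests on 205 children with results per group, 90% conversion among seronegatives, and an assumed 5 to 20% seropositive at Month 3. Within that range the literal rule lowers power to between 81 and 62%, where 6.4.1 keeps 89 to 84%. It raises error at the margin to between 3.4 and 6.4%, and gives the opposite conclusion in 12 to 29% of trials when true conversion is equal. With no seropositive children at Month 3 the two rules are identical. The effect is confined to the anti-Me and anti-Ru tests.

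**What to change.** Adopt the sponsor's own 6.4.1 definition throughout. In SAP 11.2.4 and Template 14, set N to children with a Month 3 titre below the cut-off (150 mIU/ml for measles, 4 IU/ml for rubella) and a Month 4 result. Set the rate to the share of those children at or above the cut-off at Month 4. Align protocol 10.6, and report the number seropositive at Month 3 in each group beside the test.

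Optionally, note under protocol Table 19 that the 90% power for anti-Me and anti-Ru assumes essentially all 205 evaluable children per group are seronegative. With 184 it is about 87 to 88%, depending on the method.

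The cost is one sentence per antigen in the SAP and a template footnote that has to be adapted anyway. The protocol 10.6 wording and the optional Table 19 note are protocol text, so they do need a small protocol edit. Data collection and sample size do not change. Because the study is open-label, the wording should be settled before the Month 3 and Month 4 results are seen by group.
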